- 25.1. An approved member of the study team will conduct the consent process with the participant and/or their LAR in a private area of the hospital or by phone if needed. If applicable, impartial witness will be utilized as needed (witness/translator for Spanish speaking participant and impartial witness for phone consent).
- 25.2. It may not be possible to have an in-person discussion of the study with participants or their LAR. Documenting written informed consent in these instances must involve a process as follows: the participant or their LAR receives a copy of the informed consent document in advance of a telephone discussion. The investigator obtains consent over the telephone with the participant or their LAR. If LAR consented via phone, a copy of the consent will be mailed to LAR.
- 25.3. The informed consent form may be mailed, emailed or faxed to the participant or their LAR. The consent discussion may then be conducted by telephone or in person when the subject or subject's LAR can read the consent form during the discussion.
- 25.4. Investigators will explain the study to the potential participant or their LAR by reading the informed consent document to the participant and/or LAR, providing all pertinent information (purpose, procedures, risks, benefits, alternatives to participation), and allowing the potential participant or their LAR ample opportunity to ask questions. This can be done by phone or in person.
- 25.5. Investigators will ensure a thorough verbal discussion by phone or in person of the consent form. Investigators will allow the potential participant or LAR time to read the consent form and allow the participant or their LAR sufficient time to consider whether or not to participate in the research.

PROTOCOL TITLE: Open, non-comparative pilot study to provide access to treatment with investigational convalescent plasma and measure antibody levels in patients hospitalized with COVID-19

25.6. Investigators will ensure the potential participant or their LAR additional questions s/he may have are addressed.

25.7. Participants and/or their LAR will be asked to explain the purpose of the study, procedures involved, and/or conditions for participation to confirm understanding.

25.8. If the participant or LAR agrees to participation, s/he signs the consent form and returns it to the investigator for signature and date. The signed and dated consent form can be returned to investigators by mail, facsimile, or by scanning the consent form and returning it through a secure e-mail account.

25.9. Once the signed form is received, the investigator who conducted the informed consent will sign and date the consent and will ensure the participant or their LAR receives a copy of the fully signed consent form. The fully signed original consent form will be filed with the participant's study records.

25.10. Ongoing consent from participants and and/or their LAR will be ascertained as research procedures are being conducted.

25.11. Alternately, on a case-by-case basis, and per the FDA regulation 21 CFR 50.23 Exception from general requirements, the following will be done:

(a) The obtaining of informed consent shall be deemed feasible unless, before use of the test article (except as provided in paragraph (b) of this section), both the investigator and a physician who is not otherwise participating in the clinical investigation certify in writing all of the following:

(1) The human subject is confronted by a life-threatening situation necessitating the use of the test article.

(2) Informed consent cannot be obtained from the subject because of an inability to communicate with, or obtain legally effective consent from, the subject.

(3) Time is not sufficient to obtain consent from the subject's legal representative.

(4) There is available no alternative method of approved or generally recognized therapy that provides an equal or greater likelihood of saving the life of the subject.

(b) If immediate use of the test article is, in the investigator's opinion, required to preserve the life of the subject, and time is not sufficient to obtain the independent

PROTOCOL TITLE: Open, non-comparative pilot study to provide access to treatment with investigational convalescent plasma and measure antibody levels in patients hospitalized with COVID-19

determination required in paragraph (a) of this section in advance of using the test article, the determinations of the clinical investigator shall be made and, within 5 working days after the use of the article, be reviewed and evaluated in writing by a physician who is not participating in the clinical investigation.

(c) The documentation required in paragraph (a) or (b) of this section shall be submitted to the HRRC as a Reportable New Information (RNI) within 5 working days after the use of the test article. The documentation to be used within the RNI is titled “Informed Consent Exception from General Requirements”. The form can be completed via eSignatures by utilizing the fillable form or hand written signatures by utilizing the non-fillable form.

Subjects not fluent in English

25.12 Given the public health emergency surrounding this research, non-English speaking patients may be included in the study, and this will only include Spanish speaking individuals.

25.13 The consent process will be conducted by a member of the study team fluent in the Spanish language and/or with the assistance of a qualified interpreter.

Cognitively Impaired Adults/Adults Unable to Consent/Use of a Legally Authorized Representative

25.14 Some participants are expected to be cognitively impaired, either due to a pre-existing condition, or because of conditions related to their infection with COVID-19. Cognitively impaired participants will be enrolled in the study with the consent of their LAR

The study team, in consultation with the clinical care provider, will determine if a participant has capacity to consent. Specifically, the investigators will utilize the Capacity to Consent Quiz or the GCP teach back technique with the consent form. After each section of consent form has been discussed with the participant, the investigator will ask the participant to explain their understanding of the content. Based on the results, the investigators will determine if the participant has the ability to consent.

Capacity to consent will be evaluated by the study team, in consultation with the clinical care provider, as part of the ongoing consent process as described above. If the participant regains capacity to consent, a member of the study team will conduct the consent process as described above.

PROTOCOL TITLE: Open, non-comparative pilot study to provide access to treatment with investigational convalescent plasma and measure antibody levels in patients hospitalized with COVID-19

We will obtain evidence of agency under a durable power of attorney or surrogate health decision maker status under the NM Uniform Health Care Decisions Act, NMSA 1978, 24-7A-1 et seq.

Subjects who are not yet adults (infants, children, teenagers)

N/A

Waiver or Alteration of Consent Process (consent will not be obtained, required element of consent will not be included, or one or more required elements of consent will be altered)

Waivers of consent and HIPAA authorization are requested for screening/ recruitment purposes. For the waiver of HIPAA authorization, the Data Warehouse will generate a daily list of patients with documented positive COVID-19 with their locations in the hospital. The attending will be contacted via tigerconnect to consent and start the treatment.

26. Documentation of Consent

- 26.1. For English-speaking participants (or LARs), consent will be documented using an HRRC-approved consent document.
- 26.2. For Spanish speaking participants (or LARs), a Short Form of Consent in their preferred language will be used to document consent.

27. Study Test Results/Incidental Findings

- 27.1. **Individual Results:** Results of the titers of neutralizing antibodies and nasopharyngeal SARS-CoV-2 will not be shared with the participants and their providers. The rest of routine laboratory and clinical notes will be available in the electronic medical record patient portal

28. Sharing Study Progress or Results with Subjects

- 28.1. During the study we do not intend to provide subjects with a summary of the trial. This a short, pilot study and results will be compiled at the end and then results will be informed in writing to the patients at that moment.

29. Inclusion of Vulnerable Populations

Cognitively impaired adults will be included in the study since the disease under investigation disproportionately affects older adults and/or contributes to the temporary cognitive impairment of a significant proportion of patients. To protect their rights and welfare, consent will be sought from competent ;iLAR, and participants who regain capacity to consent as (determined by the study team in consultation with clinical care providers) will be re-consented.

30. Community-Based Participatory Research N/A

31. Research Involving American Indian/Native Populations N/A

32. Transnational Research N/A

PROTOCOL TITLE: Open, non-comparative pilot study to provide access to treatment with investigational convalescent plasma and measure antibody levels in patients hospitalized with COVID-19

33. Drugs or Devices:

See section 12.1

34. Principal Investigator's Assurance

By submitting this study in the Click IRB system, the principal investigator of this study confirms that:

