There are reports that convalescent serum was used for therapy of patients with COVID-19 in China during the current outbreak. In an open label study, 5 patients received transfusion with convalescent plasma with a SARS-CoV-2– specific antibody (IgG) binding titer greater than 1:1000 (end point dilution titer, by enzyme-linked immunosorbent assay [ELISA]) and a neutralization titer greater than 40 (end point dilution titer) that had been obtained from 5 patients who recovered from COVID-19 (Shen 2020). Convalescent plasma was administered between 10 and 22 days after admission. In this preliminary uncontrolled case series of 5 critically ill patients with COVID-19 and ARDS, administration of convalescent plasma containing neutralizing antibody was followed by improvement in their clinical status.

In another study, 10 patients were treated with one dose of 200 mL convalescent plasma (CP) derived from recently recovered donors with the neutralizing antibody titers above 1:640 in addition to maximal supportive care and antiviral agents Duan 2020). The clinical symptoms were significantly improved along with increase of oxyhemoglobin saturation within 3 days. Several parameters tended to improve as compared to pre-transfusion, including increased lymphocyte counts ($0.65 \times 10^9/L$ vs. $0.76 \times 10^9/L$) and decreased C-reactive protein (55.98 mg/L vs. 18.13 mg/L). Radiological examinations showed varying degrees of absorption of lung lesions within 7 days. In none of these two trials serious adverse events associated with the use of CP were reported.

More recently, the FDA has endorsed the use of CP under an emergency IND, specific guidance on donor and potential recipient selection has been published. (<https://www.fda.gov/media/98616/download>)

Little is known about how the treatment with CP affects the recipient's immune response to the infection with SARS-CoV-2. What levels of neutralizing antibodies (NAb) are obtained in patients transfused? Is there association between neutralizing antibody titers and clinical outcomes? In the study by Duan et al, with 10 patients treated with CP, the neutralizing antibody titers of five patients increased and four patients remained at the same level after CP transfusion. However, neither study performed a comparison between the NAb dosing adjusted for body weight versus resulting NAb levels in recipients.

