3. Contraindication to transfusion or history of prior severe allergic reactions to transfused blood products
4. On ECMO or in refractory shock at entry

5. Number of Subjects

This pilot aims to explore safety and measure antibody levels in patients treated with CP. We aim to enroll 30 subjects to ensure the estimate of *neutralizing antibodies* to be within 20% margin of error.

PROTOCOL TITLE: Open, non-comparative pilot study to provide access to treatment with investigational convalescent plasma and measure antibody levels in patients hospitalized with COVID-19

6. Study Timelines

Hospitalized patients will be enrolled as soon as their COVID-19 diagnosis is confirmed, using approved diagnostic methods, and will be followed until hospital discharge or death. Patient enrollment will start immediately after IRB approval. We anticipate a 3-month enrollment. The study will continue for another 24-months after the last enrollment during which we will be able to process and analyze data, and disseminate findings.

7. Study Endpoints

7.1. Primary endpoint:

- 7.1.1. Titers of SARS-CoV-2 neutralizing antibodies measured by focus reduction neutralization test (FRNT) at days 0 (pre-transfusion), 1, 3, 7 and 14 days of CP transfusion.

- 7.1.2. Availability of convalescent plasma

7.2. Secondary endpoints:

Clinical outcomes:

- 7.2.1 Serious adverse events
- 7.2.2 SARCoV-2 viral shedding in nasopharyngeal samples determined by RT-PCR
- 7.2.3 Genomic variations of SARS-CoV-2 before and after CP transfusion
- 7.2.4 Transfer to ICU
- 7.2.5 Type and duration of respiratory support (and other ICU support including ECMO, CRRT) in ICU
- 7.2.6 Cardio-circulatory arrest (at any time)
- 7.2.7 ICU mortality and LOS
- 7.2.8 Hospital mortality and LOS
- 7.2.9 Ventilator-free days
- 7.2.10 In hospital mortality
- 7.2.11 Titer of other functions of antibodies, including antibody-dependent cell-mediated and complement-dependent cytotoxicity

7.3. Safety Endpoints:

- 7.3.1 Rapid deterioration of respiratory or clinical status on transfusion of SARS-CoV-2 convalescent plasma.
- 7.3.2 Cumulative incidence of serious adverse events during the study period: febrile non-hemolytic transfusion reaction, allergic transfusion reaction, transfusion related acute lung injury (TRALI), transfusion associated circulatory overload (TACO),

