 - 12.5.2. The anti-SARS-CoV-2 convalescent plasma will be in standard plasma blood unit bags, anticoagulated with a citrate-based anticoagulant (ACD-A, CP2D, et cetera), labeled with a specific ISBT product code, and stored in the UNM Blood Bank per FDA, AABB, and CAP protocols. Plasma transfusion will be administered over no more than four hours.

Table 1: Schedule of Events

PROTOCOL TITLE: Open, non-comparative pilot study to provide access to treatment with investigational convalescent plasma and measure antibody levels in patients hospitalized with COVID-19

Study period	Screen	Baseline	Transfusion	Follow-up			
Day	-1 to 0	0	0	1	3	7	14
Eligibility							
Informed consent	x						
Demographic and Medical history	x						
SARS-CoV-2 RT-PCR for eligibility	x						
Pregnancy test	x						
Type and screen	x						
Study Agent Administration							
Plasma Transfusion			x				
Study Procedures							
Vital signs	x	x	xxxx[1]	x	x	x	x
Physical assessment	x		x	x		x	
Symptom screen	x	x	x	x	x	x	x
Concomitant medications	x	x	x				

PROTOCOL TITLE: Open, non-comparative pilot study to provide access to treatment with investigational convalescent plasma and measure antibody levels in patients hospitalized with COVID-19

Adverse event monitoring		x	x	x	x	x	x	
Laboratory testing								
SARS-CoV-2 RT-PCR^[2] and Genomic analysis		x			x	x	x	
SARS-CoV-2 neutralizing antibody		x		x	x	x	x	
Secondary End point registration (clinical outcome)								

1. Vital sign testing: Immediately prior to infusion, 10-20 minutes after start of infusion, at completion of infusion and 30-60 minutes after the end of the infusion
2. Sampling can include nasopharyngeal, nasal or oropharyngeal swabs.

13. Data Analysis

13.1.1. We will determine whether there is a correlation between the NAb dose (in NAb units/kg body weight, where a unit is the reciprocal of the endpoint NAB titer in the CP multiplied by the volume in ml) and change or lack of change when comparing pre-treatment and day one NAb titers. We will also compare changes in pre- and post-treatment NAb titers based on NAb dosing calculated in units/BSA and units/calculated plasma volume to see if either measurement provides a better prediction of changes in NAb titers in recipients.

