13.2. Data analysis will be limited to hospitalized subjects with respiratory symptoms and laboratory confirmation of SARS-CoV-2 infection by detection RNA in upper or lower respiratory samples (nasal or oral swabs or endotracheal fluid) or blood or by detection of NAb in serum. Subjects without laboratory-confirmed COVID 19 will be excluded from analysis.

Neutralizing antibody titers in the patient's first blood sample (day 0) will be compared by rank sum (Wilcoxon) test between patients who develop any of the secondary

PROTOCOL TITLE: Open, non-comparative pilot study to provide access to treatment with investigational convalescent plasma and measure antibody levels in patients hospitalized with COVID-19

clinical end-points and patients who do not develop these secondary endpoints. The same comparison will be performed to evaluate NAb titers with other parameters such as age ≥ 65 and < 65 , presence or absence of diabetes, or presence or absence hydroxychloroquine therapy. These analyses of day 0 NAb titers aim to characterize patient heterogeneity in NAb titers in relationship to patient demographic and clinical characteristics.

We will also analyze the association between NAb titers at day 0 with duration of viral shedding, duration of hospitalization and duration of intubation and other clinical parameters.

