Our primary endpoint for statistical analysis is changes in NAb titers at day 1, 3, 7, and 14 from the entry level (day 0). Our primary hypothesis is that NAb titers will increase post-transfusion in positive correlation with transfused volume of convalescent plasma when adjusted for NAb titer in the convalescent plasma. We will use repeated measurements analysis of variance (ANOVA) or analysis of covariance (ANCOVA) when controlling for other factors (e.g. use of hydroxychloroquine) for initial exploration of the association with the transfusion volume of convalescent plasma. A more advanced approach is to use nonlinear regression models with random effects to characterize the trajectory of NAb titers over the course of 14 days. This latter approach can effectively characterize individual-specific trajectory in NAb titers in relation to convalescent plasma, and at the same time quantify between-patients variation, thereby improving statistical power. This mixed-effects nonlinear regression modeling approach is also capable of adjusting for other factors as appropriate (e.g. patient age). We will also conduct post-hoc analysis of change in NAb titers from day 0 to a specific day (day 1, 3, 7, or 14) post transfusion of convalescent plasma when appropriate. Better understanding and better characterization of the relationship between NAb titers and amount of convalescent plasma transfusion adjusted for NAb titer in the convalescent plasma will inform standardized dosage for future study.

In the absence of a comparison group, we will use descriptive statistics to report other parameters of interest (e.g. secondary outcomes), including the use of mean (SD), frequency (%) and their confidence interval. When appropriate, we will also report association between a parameter of interest and a factor of clinical relevance (e.g. duration of shading and underlying comorbidities, NAb titers at a specific post-transfusion day and underlying comorbidities, NAb titers at a specific post-transfusion day and secondary outcomes such as transfer to ICU or hospital death). This analysis will utilize odds ratio and Fisher's test for dichotomous variables, and Wilcoxon test a continuous variable.

We will conduct interim analysis after the first 10 patients complete the study. Based on the interim analysis results we may consider submitting a protocol amendment requesting adjustment our patient recruitment or CP dosing.

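### The primary dose-response analyses change in NAb titre from day 0 without stating the scale or committing to adjust for the day-0 titre; fixing both is a cheap improvement

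*Combined protocol and SAP*

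**What the plan says.** Objective 1.1.2 and section 13.1.1 correlate the NAb dose per kg (reciprocal donor titre times volume) with "change or lack of change when comparing pre-treatment and day one NAb titers". Doses per BSA and per plasma volume are then compared as predictors of the change. Section 13.2 states: "Our primary endpoint for statistical analysis is changes in NAb titers at day 1, 3, 7, and 14 from the entry level (day 0". Its hypothesis is that titres rise "in positive correlation with transfused volume of convalescent plasma when adjusted for NAb titer in the convalescent plasma".

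For method, 13.2 offers "repeated measurements analysis of variance (ANOVA) or analysis of covariance (ANCOVA) when controlling for other factors (e.g. use of hydroxychloroquine" as a first exploration. It then describes a nonlinear random-effects model that is "capable of adjusting for other factors as appropriate (e.g. patient age".

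The day-0 titre is available. Section 7.1.1 has titres "measured by focus reduction neutralization test (FRNT) at days 0 (pre-transfusion), 1, 3, 7 and 14 days of CP transfusion", and Table 1 schedules the baseline sample. Section 13.2 also studies it in its own right: "These analyses of day 0 NAb titers aim to characterize patient heterogeneity in NAb titers". It is not named as a covariate for the dose-response.

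Only the dose is given units. The text available for review states no scale for the recipient's change, no log transform, and no rule for titres below the detection limit.

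**The concern.** Titres are read from serial dilutions (section 8), so a raw difference and a log difference are both natural readings. The phrase in 13.1.1 could even mean a yes/no outcome. If the scale is left open until the data are in, the scale can decide the result.

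A change score also fixes the coefficient of the day-0 titre at 1. If the true slope of log day-1 on log day-0 titre is not 1, the dose slope carries variance that a covariate would remove. Section 13.2 concedes limited power with 30 patients, puts its focus on this hypothesis and wants the result to inform future dosing. The same outcome also decides which dose metric predicts best.

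**Working it through.** **The plan's own figure.** Section 5 gives 30 subjects for a 20% margin of error, without an SD, confidence level or scale. For a proportion of 0.5, absolute margin 0.20 and 95% confidence, n = 1.96² × 0.25 / 0.04 = 24.01, so 25. For a mean with a relative 20% margin, n=30 needs a CV of about 0.56. The figure cannot be reproduced from stated inputs, and the point below does not depend on it.

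**Variance of the dose slope.** Let λ = SD(day 1)/SD(day 0) and ρ = their correlation given dose, both on the log2 scale, and b = ρλ. In units of the day-0 variance:

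- change score: λ² + 1 − 2ρλ
- adjusted for day 0: λ²(1 − ρ²)
- difference: (1 − b)², which is zero at b = 1.

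The covariate takes residual df from 28 to 27 and multiplies slope variance by (n−3)/(n−4) = 27/26 = 1.0385. With λ = 1 and dose independent of baseline, the adjusted/change ratio is (1 + ρ)/2 × 27/26:

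| ρ (assumed) | ratio | cut in slope variance |
|---|---|---|
| 0.3 | 0.675 | 32.5% |
| 0.5 | 0.779 | 22.1% |
| 0.7 | 0.883 | 11.7% |
| 0.8 | 0.935 | 6.5% |
| 0.9 | 0.987 | 1.3% |

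**Cost if the covariate explains nothing.** The CI width ratio is √1.0385 × 2.0518/2.0484 = 1.021. If dose and day-0 titre correlate at r, this is multiplied by 1/√(1−r²), giving 1.042, 1.070 and 1.179 at r = 0.2, 0.3 and 0.5.

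**Power by simulation.** All inputs are assumptions:

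- n=30 complete pairs, two-sided 5%;
- 200 mL given; weight mean 85 kg, SD 18; plasma volume 40 mL/kg; day-1 titre by simple dilution;
- donor geometric mean 320, log2 SD 1.25;
- baseline geometric mean 40, log2 SD 2 (the high end of the range tried, 1 to 2);
- assay log2 SD 0.6; detection limit 10, lower values set to 5;
- weight independent of day-0 titre.

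| Endogenous log2 rise (mean, SD) | log2 change | adjusted |
|---|---|---|
| none | 49% | 72–73% |
| 1, 1 | 26% | 32% |
| 2, 1.5 | 14% | 14% |

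Over 729 assumed scenarios the power change ran from −2 to +38.5 points, with a median of 3.5. It was under 5 points in 412 and at least 10 in 207. These are counts of assumptions, not probabilities.

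**Scale.** Take 3000 mL recipient plasma, 200 mL given and donor titre 640 (the recipient volume and donor titre are assumed). The day-1 titre is (B × 3000 + 640 × 200)/3200 for day-0 titre B:

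| B | day 1 | raw change | log2 change |
|---|---|---|---|
| 20 | 58.75 | 38.75 | 1.55 |
| 80 | 115 | 35 | 0.52 |
| 320 | 340 | 20 | 0.09 |

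The two scales describe the same patients very differently. In the simulated trials above they disagreed on p<0.05 in about 37% (no rise), 29% (1, 1) and 17% (2, 1.5). With no rise, a lower baseline SD of 1 gave 27%.

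**The case against.** The strongest reply is that nothing in the plan blocks baseline adjustment. ANCOVA is allowed, hydroxychloroquine and age are only examples, and ANOVA/ANCOVA is labelled initial exploration ahead of a random-effects trajectory model that might use the day-0 titre in part. This stands as a limit: the power figures apply to the day-1 change analysis, not to the whole plan. It does not close the gap, because the random-effects model has no stated form and permission to adjust leaves the choice open until results are known.

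The gain is also often small, and no input to it comes from the documents. That stands. The background series, in which "the neutralizing antibody titers of five patients increased and four patients remained at the same level after CP transfusion", gives no SD or day-0/day-1 correlation.

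Under simple dilution, dose adds on the raw scale, so a log2 analysis makes the dose effect shrink as the day-0 titre rises. That stands too. The log2 choice is defensible for dilution titres, but the essential step is to fix a scale in advance.

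A reader might infer that the change analysis is confounded or biased. The documents do not support that: planned volume is 200 mL for all, and section 2 says donor titre cannot initially be measured before administration. Nor do they guarantee the opposite. Dose is not randomised and weight enters dose per kg. With an assumed weight/day-0 correlation of 0.5, the mean simulated slopes were 0.37 (change) and 0.31 (adjusted), so adjustment can move the estimate as well as its precision.

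A reader might also count chance imbalance in day-0 titre as a second harm. It is already part of the slope variance computed above.

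**Conclusion.** The point holds as a cheap improvement, not as an error that invalidates the analysis. The scale of the primary outcome is undefined, and that can change the conclusion whatever adjustment gains. The benefit of the covariate runs from nil, when the slope of log day-1 on log day-0 titre is 1, to a cut of about a third in slope variance at ρ = 0.3 with equal SDs. The simulated rise from 49% to 72–73% power should not be read as the expected gain: it assumes no endogenous rise and a wide baseline spread, and the gain disappears at a rise of 2, 1.5. The 2% ceiling on CI widening holds only if dose is independent of the day-0 titre. Every SD, correlation and rise used here is an assumption.

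**What to change.** State in 13.1.1 and 13.2:

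1. Titres are analysed as log2, with one pre-stated value for results below the detection limit and a sensitivity analysis using another.
2. The primary day-1 model regresses log2(day-1 titre) on log2(NAb dose/kg) with log2(day-0 titre) as covariate. The BSA and plasma-volume doses use the same form.
3. The later-day models also carry the day-0 titre.
4. Because planned volume is the same for everyone, the dose coefficient mainly reflects donor titre and weight. It does not isolate the volume effect named in the 13.2 hypothesis, and the text should say so.

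Optionally, report the dose effect at the quartiles of day-0 titre as a descriptive estimate with its interval. It should not be a test: simulated power for a dose-by-baseline term at n=30 was only 9% to 34%.

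The cost is analysis wording and a little extra work; no new samples or visits are needed. The day-1 model loses one degree of freedom, and a second if the optional term is fitted. Later-day models lose more if baseline slopes differ by day. Where the covariate explains nothing, slope variance rises by about 4% if dose is independent of the day-0 titre. Intervals are about 4%, 7% or 18% wider at dose/day-0 correlations of 0.2, 0.3 or 0.5.

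### Section 13.2 relates day-0 NAb to length of stay and intubation time with no rule for patients who die, so early deaths could count as short durations and weaken, hide or reverse an exploratory association.

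*Combined protocol and SAP*

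**What the plan says.** All references are to the combined protocol and SAP.

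- **The analysis.** Section 13.2 plans an association between day-0 NAb titer and "duration of viral shedding, duration of hospitalization and duration of intubation and other clinical parameters". That sentence names no test or model.
- **Methods named elsewhere in 13.2.** Secondary outcomes are to be described "including the use of mean (SD), frequency (%) and their confidence interval". A later paragraph on associations ends: "This analysis will utilize odds ratio and Fisher's test for dichotomous variables, and Wilcoxon test a continuous variable".
- **Follow-up.** Under section 6, patients "will be followed until hospital discharge or death".
- **Endpoints.** Section 7.2 lists "ICU mortality and LOS" (7.2.7), "Hospital mortality and LOS" (7.2.8) and "Ventilator-free days" (7.2.9). No rule links mortality to length of stay (LOS), and the ventilator-free measure has no time window and no score for death.
- **Objective 1.2.4** speaks of the cumulative incidence of a set of severity outcomes that includes LOS and mortality. Section 13 gives no method to match.

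The text available for review contains no competing-risk method, worst-rank score, censoring rule or restriction to survivors for these durations.

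**The concern.** Death stops the clock on both hospital stay and intubation. A patient who dies on day 5 has a 5-day stay, and so does one who goes home well on day 5. Without a rule, a short duration mixes the best and the worst results.

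Suppose low day-0 NAb goes with slower recovery and also with higher mortality. Slower recovery lengthens stays in the low-NAb patients, while their extra early deaths shorten them. The two effects work against each other. The trial could then report little or no association between NAb and duration, or one in the wrong direction, although both underlying relationships favour high NAb.

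Deaths are plausible here. The protocol refers to high COVID-19 mortality (section 19), enrols from intensive care (section 8) and makes mortality an endpoint.

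**Working it through.** **Inputs.** From the documents: 30 subjects (section 5) and follow-up to discharge or death (section 6). The plan has no figure of its own to reproduce on this point; its 20% margin of error concerns the antibody estimate. Death rates, stays and times to death are not given, so all values below are assumptions.

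**Step 1: can the direction reverse?** With constant daily hazards for discharge (d) and death (m), mean stay = 1/(d + m) and the share dying = m/(d + m).

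- High NAb, d = 0.08 and m = 0.01: mean stay 1/0.09 = 11.1 days; deaths 0.01/0.09 = 11%.
- Low NAb, d = 0.06 and m = 0.04: mean stay 1/0.10 = 10.0 days; deaths 0.04/0.10 = 40%.

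The group with slower discharge and more deaths has the shorter stay, so reversal is possible.

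**Step 2: how large is it in 30 patients?** The simulation splits patients 15/15 into low and high NAb. This is a device for sizing the effect; the plan contains no such split. Median time to discharge is 14 versus 10 days. Stays and times to death are lognormal with SD 0.6 on the log scale, and a patient who dies has the time to death as LOS. Wrong sign means that the rank-sum statistic puts the low-NAb group at the shorter stay.

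| Mortality, low vs high NAb | Median day of death | Difference in median LOS | Wrong sign |
|---|---|---|---|
| no deaths | – | 4.0 days | about 7% |
| 35% vs 10% | 14 | about 3.7 days | about 9% |
| 20% vs 10% | 7 | about 2.7 days | about 16% |
| 35% vs 10% | 7 | about 1.4 days | about 28% |
| 50% vs 10% | 7 | about 0.2 days | about 46% |

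**Step 3: a second model.** With NAb continuous, exponential hazards, n = 30 and Spearman correlation, a negative value means that higher NAb goes with a shorter stay. The hazard ratios are per SD of log NAb.

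- Discharge 1.25, death 0.5: the mean correlation with plain stay is -0.09, -0.01, +0.06 and +0.13 at 13%, 23%, 33% and 42% deaths. With deaths ranked worst it is -0.22, -0.25, -0.29 and -0.31.
- Discharge 1.5, death 0.67: plain stay gives -0.25 to -0.06 at 12% to 41% deaths. The association is weakened, not reversed on average.
- Death hazard ratio 1.0: the two analyses agree to within 0.01.

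**Step 4: what does worst-ranking gain?** At 35% versus 10% mortality with deaths at median day 7, rank-sum power (two-sided 0.05) is about 7% for plain LOS and 53% with deaths ranked worst. With no deaths it is only 29%. Much of the 53% is therefore the assumed mortality difference entering a composite outcome. With 20% mortality in both groups, worst-ranking gives about 15% against 19% for plain LOS, which is no gain.

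**The case against.** A reader might infer that the plan prescribes a Wilcoxon test on plain durations. The documents do not say so. The sentence on day-0 NAb and durations names no method. The rank-sum test earlier in 13.2 compares NAb between patients with and without clinical endpoints, and the later Wilcoxon sentence closes a different list of examples. What stands is narrower: no death rule is given, and the only tools named for continuous outcomes take no account of death.

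The analysis is also declared exploratory, with a false discovery rate adjustment and an admission of limited power. Hospital and ICU mortality are separate endpoints, and NAb is to be related to clinical endpoints including hospital death. A mortality gradient would therefore appear beside the durations. This lowers the stakes, but neither the multiplicity adjustment nor a separate mortality table corrects a duration result that points the wrong way.

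Two objections bear on the remedy, and both are right. The first scenario with deaths at day 7 implies only 15 × 0.35 + 15 × 0.10 = 6.75 deaths, which is thin for regression. Ranking every death worst would also assign the longest intubation to patients who died without being intubated.

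**Conclusion.** The point holds as a gap in the plan with a foreseeable consequence. If the durations are analysed as they stand, early deaths count as short durations, and the association with day-0 NAb is attenuated and may be hidden or reversed. This needs NAb to be related to mortality, and deaths to be neither rare nor late.

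Under the stated assumptions, a 4-day difference in median LOS falls to between about 3.7 and 1.4 days, with the wrong sign in about 9% to 28% of trials. Some 7% would occur with no deaths at all. Near-complete cancellation (0.2 days) needs 50% mortality in the low-NAb group. None of these rates comes from the documents.

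A reader might infer that reversal is the expected result, or that the trial's main conclusion is at risk. Neither is supported: weakening is the more common outcome in these scenarios, and the primary analysis of NAb change does not use these durations.

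**What to change.** Add a paragraph to 13.2:

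1. **Hospital stay.** Analyse time to discharge alive with death as a competing event, using cumulative incidence curves; this also gives objective 1.2.4 a method. Alternatively, use a rank test on day-0 NAb with in-hospital deaths ranked worst, labelled as a composite of stay and mortality.
2. **Intubation.** Restrict to intubated patients and analyse time to extubation alive in the same way.
3. **Description.** Report LOS and intubation duration separately for survivors and for patients who died.
4. **Regression.** Treat any model as exploratory, because few deaths are expected in 30 patients.

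The ventilator-free measure should be given a fixed window and a score for death at the same time.

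The cost is slightly more analysis work, plus recording extubation dates if they are not already captured; section 7.2.5 asks for duration of respiratory support, but no extubation date is listed. The worst-rank version answers a composite question rather than one about duration alone. Treatment, visits and sample size do not change.
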